## **6.0 Local Number of Subjects**

6.1 *Indicate the total number of subjects who will be enrolled or records that will be reviewed through Upstate.*

No more than 18 total participants (six per group)

6.2 *If applicable, indicate your screen failure rate, i.e., how many subjects you expect to screen to reach your target sample.*

54 (anticipate that for every three women screened, one will participate in the study)

6.3 *Justify the feasibility of recruiting the proposed number of eligible subjects within the anticipated recruitment period. For example, how many potential subjects do you have access to? What percentage of those potential subjects do you need to recruit?*

The feasibility of recruitment is part of what is being investigated in this pilot project and findings from this project will inform the recruitment plan of the future large intervention study. The plan for the pilot is to recruit no more than 18 (six per group) low risk pregnant women with a singleton pregnancy from Syracuse Community Health Center (50%), University OB/GYN Associates, and Upstate Community OB/GYN. All women will be enrolled during the 1st trimester (6 to 13-weeks' gestation) and without absolute contraindications to moderate intensity exercise during pregnancy as defined by American College of Sports Medicine (ACSM) and American College of Obstetricians and Gynecologists (ACOG). All participants will be cleared for exercise by their OB/GYN.

## 7.0 Inclusion and Exclusion Criteria

7.1 *Describe, in bullet points, the criteria that define who will be included in this study:*

- Adult pregnant women (i.e. 18 years of age and older)
- Low risk, singleton pregnancy
- In first trimester of pregnancy (6 to 13 weeks gestation)
- Without absolute contraindications to moderate intensity exercise during pregnancy as defined by the American College of Obstetricians and Gynecologists
- Exercise clearance from OB/GYN

7.2 *Describe, in bullet points, the criteria that define who will be excluded from this study:*

- Pregnancies greater than low risk for any reason
- Pregnant with more than one fetus
- Absolute exercise contraindications and/or lack of exercise clearance from OB/GYN

7.3 *Indicate whether you are specifically recruiting or targeting any of the following special populations in your study using the checkboxes below.*

- Adults unable to consent (*complete and upload Supplemental Form A*)
- Minors (under 18 years old)
- Pregnant women
- Prisoners

6.4 *Indicate if you will include minorities (American Indians, Alaskan Native, Asian, Native Hawaiian, Pacific Islander, Black [not of Hispanic origin] and Hispanic) as Federal mandates require that you include minorities unless you can justify their exclusion*

- Yes
- No, Justify:

## **8.0 Vulnerable Populations**

8.1 *For research that involves pregnant women, review, complete and upload Supplemental Form B: Research Involving Pregnant Women, Fetuses, or Neonates.*

- Confirmed
- N/A: This research does not involve pregnant women.

8.2 *For research that involves neonates of uncertain viability or non-viable neonates, review, complete and upload Supplemental Form B: Research involving Pregnant Women, Fetuses, or Neonates.*

- Confirmed
- N/A: This research does not involve non-viable neonates or neonates of uncertain viability.

8.3 *For research that involves prisoners, review, complete and upload Supplemental Form C: Research involving Prisoners*

- Confirmed
- N/A: This research does not involve prisoners.

8.4 *For research that involves minors (under 18 years), review, complete and upload Supplemental Form D: Research involving Minors*

- Confirmed
- N/A: This research does not involve minors (under 18 years),

8.5 Consider if other specifically targeted populations such as students, employees of or educationally or economically disadvantaged persons are vulnerable. Provide information regarding their safeguards and protections, including safeguards to eliminate coercion or undue influence.

- N/A

## 9.0 Eligibility Screening

9.1 Describe screening procedures for determining subjects' eligibility. Screening refers to determining if prospective participants meet inclusion and exclusion criteria. Include (upload) all relevant screening documents with your submission (e.g. screening protocol, script, questionnaires).

Protocol: Interested pregnant women (responding to internet requests for participants or posted flyers) will be contacted by phone or email to answer questions about the study and to verify eligibility for the study (i.e. inclusion, exclusion criteria). Participants that are interested in registering for the study will be required to get exercise clearance from their OB/GYN before being randomized into one of the three groups and then beginning that group's exercise protocol.

Clearance for participation must be provided by the participant's OB/GYN (not primary care physician or non-physician providers)

- N/A: There is no screening as part of this protocol.

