## **11.0 Research Methods & Procedures**

Provide a detailed description of the methods and procedures that will be used to carry out the study. Include a summary of study visits and procedures (i.e., schedule of events table) in the space below or as an attachment.

Please make sure to include:

- Dosing of drugs and other details of study drug administration and study treatments
- A list and description of any experimental procedures
- A list and description all tests & procedures that would no be done if the subjects were not in the study
- An explanation how study participation differs from the standard of care
- Procedures being performed to monitor subjects for safety or to minimize risks

Eighteen low risk pregnant women with a singleton pregnancy will be recruited for this pilot project from Syracuse Community Health Center (50%), University OB/GYN Associates, and Upstate Community OB/GYN. All women will be enrolled during the 1st trimester (6 to 13-weeks' gestation) and without absolute contraindications to moderate intensity exercise during pregnancy as defined by American College of Sports Medicine (ACSM) and American College of Obstetricians and Gynecologists (ACOG). All participants will be cleared for exercise by their OB/GYN. The ACSM and ACOG guidelines include 150 min/wk of cardiovascular activity at a moderate intensity; 2-3 days/week of resistance training; and 2-3 days/wk of flexibility training. Clearance will come exclusively from the OB/GYN.

Women will be randomly assigned to either UA, EX or HOMEEX. Women randomized to EX will attend three exercise classes/week at the Institute for Human Performance (IHP) and given flexibility to attend classes between the hours of 7:30a-6p, Mon-Fri. Each session will consist of: 5-min flexibility warm-up and cool-down; 40 min of moderate intensity calculated as 40-59% Heart Rate Reserve (HRR) along with Rating of Perceived Exertion (RPE) between 13-14; and 20 minutes of resistance with an additional 30 minutes of unsupervised home aerobic activity per week. The women will be given their choice of aerobic equipment or walking either track/treadmill to achieve a total of 40 minutes of moderate intensity exercise.

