Women assigned to HOMEEX will receive instructions for their home walking program including tips for walking indoors and outdoors, exercise handouts for warm-up/cool-down activities, demonstrations for resistance training activities and an exercise log. HOMEEX women will be contacted twice per week to discuss their progress, barriers/challenges faced, ask questions, and strategies to achieve the exercise guidelines. If women in either EX or HOMEEX are unable to achieve 30-40 minutes of continuous aerobic exercise at the start of the study, they will be given an individualized, progressive exercise program that breaks activity into smaller 10 minute sessions and/or increases rest between sessions to achieve the 150 minutes/week of moderate intensity activity.

Both exercise groups will receive exercise counseling during their first meeting in addition to materials on the benefits of exercise, a log to record additional activity completed each week, goal setting, making time for exercise/making exercise a habit and exercise behavioral strategies. The UA group will receive an exercise log to record any weekly activity in addition to a weekly phone call/text/email to remind the individual to download information from the Polar Ignite watch (Bethpage, NY) and a reminder to complete the weekly exercise log.

Each woman enrolled in the study will be given a Polar Ignite watch to wear for the study duration. This monitor will be programmed for moderate intensity HRR and will alarm if HR falls above/below during exercise for both exercise groups. In addition, the monitor will record all other activity within the HRR range and will be used to verify information obtained from activity and QOL questionnaires to reduce self-reported bias in all groups. For the control group, the watch will record activity by HR intensity level that can be quantified on a weekly basis.

Regardless of randomization, all women will report to the IHP between weeks 11-13 (late 1st trimester) for baseline testing and to review past medical history, medications and exercise history. Height will be measured to the nearest 0.25 inch using a stadiometer and converted to meters. BMI will be calculated using the self-reported pre-pregnancy weight. Gestational weight gain will be calculated from subtracting the pre-pregnancy weight from weight at the last obstetrics visit prior to delivery. All women will also perform a submaximal Balke-Ware

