submaximal treadmill test to determine HRR for the two exercise groups and estimate VO2max using the Pollock equation which will be repeated at 3- and 6-months after birth to compare aerobic fitness levels.

All women will complete the following questionnaires at baseline (late 1st trimester), 25-26 weeks (late 2nd trimester), and 37-38 weeks (late 3rd trimester), and monthly through 6-months post-natal: MFI, SF-12 QOL; PSQLI; CES-D; EPDS; and the PPAQ. All questionnaires have been demonstrated to have good validity, reliability, and internal consistency and the CES-D and EPDS are similar to each other in regards to internal consistency and test-retest reliability.

Infants from mothers in all three groups will have their gross and fine motor, and cognitive development measured monthly (months 1-6) at home using the Bayley Scales of Motor Development, 4th edition. The Bayley 4 is a standardized, norm-referenced tool with subtest level scaled scores, domain level composite scores, percentile ranks, and developmental age equivalents. Infant height and weight will be measured monthly through 6-months of age.

Women assigned to EX will have all of their supervised pregnancy exercise sessions, questionnaires, and weight measured at the IHP. After delivery, women assigned to EX will resume their supervised IHP exercise program between 4-8 weeks (depending on delivery mode) when they are cleared for activity by their physician, complete exercise testing at 3- and 6-months and will have monthly home visits for infant testing through 6 months. HOMEEX and UC women will visit the IHP at baseline, 3 & 6-months post-delivery for exercise testing, questionnaires, and weight measurement. HOMEX and UC groups will receive home visits for: 2nd & 3rd trimester questionnaires and weight measurement and every month post-delivery for questionnaires, weight measurement and infant testing.

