- Pregnancy Physical Activity Questionnaire
- Short-Form 12 (SF-12) Health survey
- Pittsburgh Sleep Quality Index
- Multidimensional Fatigue Inventory
- Edinburgh Post-Natal Depression Scale
- Center for Epidemiologic Studies Depression Scale

Activity	2020 September to December	2021 January to April	2021 May to August	2021 September to December	2022 January to April	2022 May to June
Recruitment (6 UC, 6 EX, 6 HOMEEX)	X					
Maternal Interventions	X	X	X	X	X	
Maternal Baseline Measurements	X	X				
Maternal Prenatal Measurements	X	X	X			
Maternal Post Natal Measurements			X	X	X	
Infant Measurements			X	X	X	X
Data Analysis				X	X	
Dissemination of results						X
First publication submission					X	
Target grant submission						X

*List, and upload, any instruments or measurement tools used to collect data (e.g. survey, scripts, questionnaire, interview guide, validated instrument, data collection form).*

*11.2 Describe any source records that will be used to collect data about subjects (e.g. school records, electronic medical records).*

n/a

*11.3 Describe whether individual subject results (such as results of investigational diagnostic tests, genetic tests, or incidental findings) will be shared with subjects or others (e.g., the subject's primary care physicians) and if so, describe how it will be shared.*

Participants will have access to the results of their testing immediately if requested but a summary of information will be provided to each participant at the end of their participation in the study.

Participants will independently choose if they wish to share any of their results with their primary care physician/OB/GYN

*11.4 Indicate whether or not generalized study results will be shared with subjects or others, and if so, describe how these will be shared.*

Overall (generalized) study results will be shared with participants at the completion of the study via an electronic and/or hard copy summary of results/findings.

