## 12.0 Study Timelines

*12.1 Describe the anticipated duration of the study needed to enroll all study subjects.*

The plan is to enroll all study participants in three months.

*12.2 Describe the duration of an individual subject's participation in the study. Include length of study visits, and overall study follow-up time.*

Each participant's time in the study will be 15 months +/- 4-8 weeks (depending on what point in the first trimester a participant begins)

*12.3 Describe the estimated duration for the investigators to complete this study (i.e. all data is collected and all analyses have been completed).*

The time from first recruitment to wrap up of this phase of the project is estimated to be 22 months.

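### The protocol does not require baseline testing before randomisation, so a woman enrolled before week 11 may already know her arm when her baseline is measured

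*Combined protocol and SAP*

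**What the plan says.** Section 9.1 gives the only written sequence. A woman who wants to take part must have OB/GYN clearance "before being randomized into one of the three groups and then beginning" her group's exercise protocol. Clearance is the only stated precondition for randomisation. Section 4.1 names the randomisation tool but gives no time point.

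Section 11.0 sets the entry window: "All women will be enrolled during the 1st trimester (6 to 13-weeks' gestation". It sets a narrower window for baseline: "Regardless of randomization, all women will report to the IHP between weeks 11-13 (late 1st trimester) for baseline testing". The questionnaires follow the same timing: "All women will complete the following questionnaires at baseline (late 1st trimester". The fitness measure at that visit is a "submaximal treadmill test to determine HRR for the two exercise groups", so it also supplies the exercise intensity. On counselling, Section 11.0 says: "Both exercise groups will receive exercise counseling during their first meeting". It does not say whether that meeting is the baseline visit or comes before it.

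Section 2.1 makes it part of the scientific endpoint to show that the measures can detect change in all three groups. Section 5.1 examines this with Friedman's test within groups and Kruskal-Wallis between them.

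**The concern.** Women cannot be masked to whether they attend classes, exercise at home or carry on as usual. If allocation comes first, an early entrant completes the treadmill test and six self-reported questionnaires knowing her arm. If she is in an exercise arm, she may also have been counselled on exercise habits and goals. Self-reported activity (PPAQ) and mood (CES-D, EPDS) are the measures most open to this. The testers may know her arm too: Section 14.3 has the same study staff supervise the supervised-exercise arm, run the fitness tests and collect the questionnaires.

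The baseline value is the reference for every later change. If allocation has already shifted it, the pilot's reading of whether an instrument detects change is blurred, and by different amounts in different arms. A woman who leaves between allocation and baseline also takes one of the six places in her arm and contributes no treadmill or questionnaire value.

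**Working it through.** The plan gives no figure for the interval between randomisation and baseline, so there is none to reproduce. The check is date arithmetic plus a comparison of the relevant sections.

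**Inputs.** Enrolment week *e* runs from 6 to 13 (Sections 6.3, 7.1 and 11.0). Baseline week runs from 11 to 13 (Section 11.0). There are six women per arm, 18 in all (Section 6.1). Assumption: randomisation follows clearance at enrolment, which is the order in Section 9.1.

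**Formula.** Shortest gap = max(11, *e*) − *e*. Longest gap = 13 − *e*.

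| Enrolled at week | Shortest gap (weeks) | Longest gap (weeks) |
|---|---|---|
| 6 | 11 − 6 = 5 | 13 − 6 = 7 |
| 8 | 11 − 8 = 3 | 13 − 8 = 5 |
| 10 | 11 − 10 = 1 | 13 − 10 = 3 |
| 11 | 11 − 11 = 0 | 13 − 11 = 2 |
| 12 | 12 − 12 = 0 | 13 − 12 = 1 |
| 13 | 13 − 13 = 0 | 13 − 13 = 0 |

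Under that assumption, a gap is certain for entry at weeks 6-10, possible at weeks 11-12 and absent at week 13. The documents do not say how entry will spread over the window, so the number enrolled before week 11 could be 0 to 18. One woman lost in the gap is 1/6 = 17% of her arm.

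**Sections side by side.** Section 9.1 goes from clearance to randomisation to the group's programme. Section 11.0 brings all women to baseline irrespective of randomisation, and describes the baseline visit by arm for the home-exercise and control women. Read together, these allow allocation before baseline and on balance suggest it. None of them states it.

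**What does not depend on reading intent.** No sentence in the protocol would be breached by randomising a woman at week 6 and testing her at week 13. That is enough to justify fixing the order.

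**The case against.** The strongest reply is that the order is inferred. Section 9.1 concerns eligibility and is not a visit schedule. The phrase about randomisation in Section 11.0 may mean only that every arm attends. Sections 24.3 and 24.4 put consent at the first visit, in an office at the Institute for Human Performance (IHP), and Section 11.0 lists baseline as the only IHP visit before delivery for home-exercise and control women. Consent, baseline and randomisation could therefore share one visit. That reading is open: screening is by phone or email, and the protocol does not define enrolment. It stands as a reason not to assert that women *are* randomised first. It does not supply the missing instruction.

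Three stronger readings are tempting and should not be drawn.

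- **The calendar proves allocation comes first.** A reader might cite the timeline row "Recruitment (6 UC, 6 EX, 6 HOMEEX", marked only for September to December 2020 while baseline measurement runs into 2021, or the participation time of "15 months +/- 4-8 weeks (depending on what point in the first trimester a participant begins". Both show at most that recruitment can precede baseline. The arm counts may be the planned split, the calendar blocks are mostly four months wide, and the duration is approximate. Both entries could read the same with randomisation after baseline.
- **Baseline is contaminated by training.** Intensity is set as a share of heart rate reserve (HRR), which comes from the baseline test, and the watch is programmed to that range. Exercise as prescribed therefore naturally waits for the test. Early exercise is not excluded, because Section 9.1 names the programme as the next step, but it is the less likely reading.
- **Losses in the gap can be quantified.** The documents give no loss rate and no count of early entrants, so a probability of losing a woman would rest on invented inputs.

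The consequence is also limited. This is an 18-woman feasibility study with no confirmatory comparison. Gestational weight gain starts from pre-pregnancy weight and is unaffected. All later questionnaires are answered with the arm known, whatever the order. An early dropout still informs retention under Aim 1.

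**Conclusion.** The point holds as an unspecified order with a sensible default, not as a demonstrated error. The protocol permits, and on balance suggests, randomisation 5-7 weeks before baseline for a week-6 entrant, shrinking to none at week 13. This rests on allocation following clearance at enrolment, which no section confirms. The likely effect is that some women know their arm, and perhaps have been counselled, when reference values are taken, chiefly the self-reported ones. Its size cannot be estimated from the documents. It merits consideration because the correction is cheap and protects the baseline on which the change analyses rest.

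**What to change.** In Sections 9.1 and 11.0, state that randomisation takes place at the end of the weeks 11-13 visit, once the treadmill test and all questionnaires are complete. Arm-specific counselling, programming of the watch and exercise then follow. Enrolment can still open at week 6. Reword Section 6.1 so that the 18 women, six per group, are counted at randomisation. Report losses between enrolment and randomisation separately, as feasibility data.

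If the sponsor intends exercise to begin before week 11, take the baseline measures at enrolment, before randomisation. Baseline would then spread over 13 − 6 = 7 weeks of gestation, compared with 13 − 11 = 2 weeks now.

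The main change adds no test, and it adds no visit provided that consent is not moved to a separate earlier IHP visit. Its costs are small. Women entering before week 11 learn their arm 1-7 weeks later, which may cost some interest. The change does not prevent early losses but moves them ahead of allocation, so a woman or two more may need to be enrolled. At an assumed 5% loss, 18/0.95 = 18.9, so 19 women; at an assumed 10%, 18/0.90 = 20.

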## 10.0 Recruitment Methods

- N/A: Subjects will not be recruited.

10.1 Describe source of subjects: When, where, and how potential subjects will be recruited.

*NOTE: Recruitment refers to how you are identifying potential participants and introducing them to the study; for example, physician referral, database search, reviewing medical records, research participant groups/help/advocacy groups, advertising companies, call centers, in person announcements / presentations, etc.*

Participants will be recruited via physician referral, posted flyers and internet postings (e.g. local mom's groups, Upstate announcements, Department of Physical Therapy Education Facebook page, etc)

*10.2 Describe how you will protect the privacy interests of prospective subjects during the recruitment process.*

*NOTE: Privacy refers to an individual's right to control access to him or herself. This is NOT asking about confidentiality of data.*

All screening and information exchanges with prospective participants will happen in private (in a one on one setting).

*10.3 Identify all materials that will be used to recruit subjects and upload copies of these documents (such as telephone scripts, flyers, questionnaires, posters, letters, e-mails, pamphlets, advertisements).*

Flyers, e-mails

